## Recruitment Procedures

Describe settings where recruitment will occur

We will be specifically recruiting via advertisements for patients who feel depressed as well as slowed down physically and mentally. Advertisements will include research flyers and brochures posted around CUMC, advertisements in local newspapers and on radio stations, information posted on departmental websites, and flyer mailings. For direct clinical or research referrals, a clinical staff member known to the patient will approach him/her and raise the possibility of study participation. We would also like to implement Columbia University's RecruitMe website as a recruitment method.

How and by whom will subjects be approached and/or recruited?

If the patient expresses a potential interest in participating, he/she will then be scheduled for a full evaluation with a study clinician. The nature of the study will be thoroughly reviewed with its risks, benefits, and alternatives to participation, and subjects' questions regarding the study will be answered. Subjects will be notified that they may leave the study at any time. Informed consent will be obtained in a private research office. A study clinician will review study procedures and the consent form with each potential participant. Each individual may take as much time as they like to decide if they do or do not wish to participate. The consent form specifies (and the study coordinator emphasizes) that participation is voluntary and withdrawal after signing consent will not affect future care. Subjects will be given a copy of the consent form, and the original will become part of the clinical record.

How will the study be advertised/publicized?

Advertisements will include research flyers and brochures posted around CUMC, advertisements in local newspapers and on radio stations, and information posted on departmental websites. Advertisements will also include research flyers mailed out individuals whom will primarily come from consumer marketing databases, which are compiled using public information, surveys, subscription information, home owner information, and phone directory information.

Do you have ads/recruitment material requiring review at this time?

Yes

Does this study involve a clinical trial?

Yes

YOU MUST REGISTER AT [ClinicalTrials.gov](https://clinicaltrials.gov) IMMEDIATELY UPON RECEIPT OF IRB APPROVAL AND **PRIOR TO ENROLLMENT** OF THE FIRST SUBJECT. YOU WILL BE PROVIDED WITH A NCT REGISTRATION NUMBER ON REGISTRATION. PLEASE REVISE THIS SECTION OF THE PROTOCOL SUMMARY FORM TO INCLUDE THE NCT NUMBER AND RE-SUBMIT AS AN AMENDMENT TO THE IRB.

**Concurrent Research Studies**

Will subjects in this study participate in or be recruited from other studies?

Yes

Describe concurrent research involvement

Subjects completing IRB #6836 ([name] PI) who meet the selection criteria for this study will be offered participation. Additionally, subjects who are currently participating in #7289R, #7409, #7360, #7489, and/or #7379 and meet the selection criteria for this study will be offered participation. Only an investigator not directly involved with an eligible subject’s care will approach the subject to describe this protocol and have an informed consent discussion.

**Inclusion/Exclusion Criteria**

Name the subject group/sub sample

Patients

Create or insert table to describe the inclusion criteria and methods to ascertain them

Criterion	Method of Ascertainment
1. Age >59 years	1. Interview
2. DSM 5 non-psychotic Major Depressive Disorder, Dysthymia, or Depression Not Otherwise Specified	2. Clinical interview and SCID
3. Center for Epidemiological Studies Depression (CES-D) Rating Scale >9	3. CES-D
4. decreased processing speed (defined as performance > 0.5SD below age-adjusted norms on Digit Symbol Substitution Test or Trail Making Test Part A) OR decreased gait speed (defined as average walking speed over 15’ course < 1m/s)	4. Digit Symbol Substitution Test, Trails A, timing of walking speed
5. willing to and capable of providing informed consent and complying with study procedures	5. Clinical interview
6. Alternative standard treatments for MDD, Dysthymia, or Depression NOS (e.g., antidepressant medication or psychotherapy) have been discussed and the individual agrees to be involved in an experimental treatment.	6. Clinical interview

Create or insert table to describe the exclusion criteria and methods to ascertain them

Criterion	Method of Ascertainment
-----------	-------------------------

1. diagnosis of substance abuse or dependence (excluding Tobacco Use Disorder) within the past 12 months

1. Clinical interview and SCID

2. history of or current psychosis, psychotic disorder, mania, or bipolar disorder

2. Clinical interview and SCID

3. diagnosis of probable Alzheimer's Disease, Vascular Dementia, or PD

3. Clinical interview, MMSE for AD and VD. PD will be ruled out by satisfying (1) and (2) and (3 or 4) below:

(1) patient gives no history of PD during clinical interview

(2) patient's primary doctor gives no history of PD

(3) there are no signs of PD on physical exam in the LLDC

(e.g., absence of asymmetric resting tremor, decreased arm swing, soft voice, decreased facial expression, difficulty rising from chair, dystonia)

(4) If a patient does have one or more signs of possible PD on exam as per (3), [name] (study neurologist)

will come examine the patient and comment on whether PD can be ruled out or whether PD is possible and patient needs further neurologic work up.

4. Mini Mental Status Exam (MMSE) < 25

4. MMSE

5. Total HRSD  $\geq$  25, HRSD suicide item > 2, or the presence of significant suicide risk as judged by clinician.

5. Clinical interview, HRSD, CGI

pasting. HRSD suicide item > 2

or Clinical

Global

Impressions

(CGI)-Severity

score of 7 at

baseline.

6. current or recent (within the past 4 weeks) treatment with

antidepressants, antipsychotics, dopaminergic agents, or mood stabilizers

6. Clinical interview

7. history of allergy, hypersensitivity reaction, or severe

intolerance to L-DOPA

7. Clinical interview

8. acute, severe, or unstable medical or neurological illness

8. Clinical interview, physical exam, EKG

9. mobility limiting osteoarthritis of any lower extremity joints, symptomatic

lumbar spine disease, mobility limiting history

of joint replacement surgery, or history of spine surgery

9. Clinical interview, physical exam

FOR SUBJECTS

FOR SUBJECTS

RECEIVING

PET/MRI

SCANS ONLY:

10. having  
contraindication  
to MRI scanning  
(such as metal in  
body) or unable  
to tolerate the  
scanning  
procedures

10. MRI safety screening form

11. history of  
significant  
radioactivity  
exposure  
(nuclear  
medicine studies  
or occupational  
exposure)

11. Clinical interview

### Waiver of Consent/Authorization

Indicate if you are requesting any of the following consent waivers

Waiver of consent for use of records that include protected health information (a HIPAA waiver of Authorization)

No

Waiver or alteration of consent

No

Waiver of documentation of consent

No

Waiver of parental consent

No

### Consent Procedures

Is eligibility screening for this study conducted under a different IRB protocol?

Yes

Indicate NYSPI IRB #

6395R

Describe Study Consent Procedures

Following the study screening procedures, a study clinician authorized to obtain patient consent will explain

the study procedures along with the attendant risks, benefits, and alternatives, including the anticipated outcome of doing nothing. The study clinician will then leave the room while the potential subject reads the consent form and return to answer any questions the subject has. During the consent discussion, individuals will be offered the option to take the consent home to discuss with family and/or physician prior to signing it. Subjects who wish to participate will sign the consent form, while those who do not wish to participate will receive appropriate referrals.

Indicate which of the following are employed as a part of screening or main study consent procedures

✓ Consent Form

**Study Procedures**

Describe the procedures required for this study

Evaluation

1. Every subject evaluated for this protocol will receive a clinical interview by a psychiatrist or psychologist. **A psychiatrist or other qualified physician will see participants to evaluate medical aspects of eligibility, including screening for signs or symptoms of Parkinson’s Disease (PD). If there is any concern, they will be referred to a neurologist.** Additional assessments will be administered by a trained rater (BA, RN, or SW) in the LLDC, including the Center for Epidemiologic Studies Depression Scale (CES-D) and the 24-item Hamilton Rating Scale for Depression (HRSD), and have a SCID performed by a trained rater. If a subject has a diagnosis of Major Depressive Disorder (MDD) or Dysthymia, he/she will be informed of this and educated about the availability of treatments for depression. If a subject is not interested in depression treatment and/or prefers to begin with an experimental treatment for slowing and depression, he/she will be offered participation in the present study provided their HRSD < 25 and there is no suicidal ideation present. Severe MDD (i.e., HRSD ≥ 25) and/or the presence of significant suicide risk (e.g., HRSD suicide item > 2, clinician judgement that there is significant risk of suicide) are exclusions for this study. Patients with Depression NOS will be educated that as yet, there are no FDA-approved treatments for their condition. Based on the extant data supporting the efficacy of antidepressants for MDD and Dysthymia, they will be informed that antidepressant treatment would be a very reasonable option for their condition. These potential subjects will be offered the option of being referred out for depression treatment, and it will be clarified that L-DOPA is not as yet a treatment for MDD. Thus, all potential participants in this study must state their preference not to be treated with a standard treatment for depression.

2. Next, trained raters (BA, RN, or SW) in the LLDC will assess processing speed using Digit Symbol test from the WAIS-III, the Trail Making Test Part A, the Pattern Comparison Test, and the Letter Comparison Test. Previous research established that these tests were all reliable and valid (moderate to high loadings on the latent speed factor). Digit Symbol or Trails A will be used as a selection criterion, with patients included in this study if they scored 0.5 SD below the age-adjusted norms on Digit Symbol or Trails A. A latent factor (and subsequent factor score) will be extracted from the 3-test battery pre- and post-treatment and used as the main outcome in this pilot study. By extracting a latent factor and factor loadings we will utilize a more pure measure of processing speed for pre- post-testing than if we used the raw scores from an individual test or a sum total score from the three raw scores combined.

3. Patients' gait will be assessed by trained raters as walking speed in m/s on a Gaitrite walkway system. Patients are instructed to walk at their usual or normal speed starting and ending at a point 6 feet prior to and after the walkway course to eliminate acceleration and deceleration effects. Two trials will be completed, and gait speed will be based on the average of 2 trials. Gait speed will be used as a selection criterion, with patients included in this study if they have a gait speed < 1 m/s.

4. If subjects are eligible for the study after review of their processing speed and gait speed and decide to participate by signing informed consent, then they will complete the remainder of the baseline assessment. This includes recording of each subject's chief complaint, referral source, age of onset of mood and/or cognitive decline, number prior depressive episodes, age, sex, marital status, race and ethnicity, years of education, employment status and income, years of education, family history. We also will document medical history, physical exam, urine drug screen, CBC, chemistries and electrolytes, thyroid profile, vitamin B12 and folate levels, urine analysis, and ECG. Vital signs will be measured at baseline and monitored weekly throughout the study. The Cumulative Illness Rating Scale-Geriatric (CIRS-G) (112) will be filled out at baseline to measure chronic medical illness burden. Subjects' current physical pain will be assessed weekly using a 100mm Pain Visual Analog Scale (VAS) and used as a covariate in analyses of gait speed (113).

5. Baseline markers of inflammatory status will be added to the serum assessments detailed above, including C-reactive protein (CRP), IL-6, and Tumor Necrosis Factor  $\alpha$  (TNF $\alpha$ ). The rationale for inflammatory marker measurement is evidence that dopaminergic dysfunction in older adults may be caused by the chronic, low-grade inflammatory process concomitant with aging ("inflammaging") (151). Pro-inflammatory cytokines such as IL-6 may reduce dopaminergic transmission in multiple ways, including decreasing dopamine synthesis by limiting tetrahydrobiopterin (BH4) availability, impairing vesicular release of dopamine in presynaptic neurons by decreasing expression of vesicular monoamine transporter 2 (VMAT2), increasing DAT reuptake of synaptic neurotransmitter, and decreasing glutamate-dependent dopamine signaling (152).

6. Other neuropsychological measures completed at baseline include trained study rater (BA, RN, SW) assessment of episodic memory functioning using the Wechsler Memory Scale Logical Memory Test I & II (153). Inclusion of this test will allow us to identify deficits in episodic memory functioning consistent with a classification of amnesic mild cognitive impairment (aMCI) (7). Executive function will be assessed via the NIH-EXAMINER battery designed to assess executive functions reliably, comprehensively, and efficiently (154-155). This battery examines working memory, inhibition, set shifting, fluency, insight, planning, social cognition and behavior. Confirmatory factor analysis supports both a one-factor model and

a three- factor model, and these models formed the basis for an Executive Composite score and subscales scores for Working Memory, Cognitive Control, and Fluency.

7. Domains of function assessed by trained study raters (BA, RN, SW) at baseline include: the Short Physical Performance Battery (SPPB) (156), a performance measure of gait, balance, and lower extremity strength sensitive to meaningful change. The 36-item self-report World Health Organization Disability Assessment Schedule 2.0 (WHODAS2) provides a global measure of disability and 7 domain-specific scores based on the conceptual framework of the International Classification of Functioning, Disability, and Health (ICF) (157). The self-report 38-item Measure of Everyday Cognition (ECog) is adapted from an informant-report version and measures impairment and change in domains of everyday/real-world functioning relevant to 7 specific neuropsychological domains (158). The Falls Efficacy Scale-International will assess subjects' fear of falling weekly using a 16-item scale rating respondents' confidence (1 not at all concerned—4 very concerned) in doing daily tasks without falling (159-160).

8. Finally, aliquots of peripheral blood will be frozen for subsequent DNA isolation and determination of interleukin-6 (IL-6) and catechol-O-methyl-transferase (COMT) genotype. These genotypes will be analyzed in exploratory analyses to determine their effects on baseline dopamine functioning and response to L-DOPA.

### MRI Scanning

9. N=30 subjects of the total N=90 sample will undergo neuroimaging. The first 30 subjects who are eligible/safe for PET/MRI procedures and are willing to be scanned will be offered participation in these procedures. Subjects who are not willing or able to participate in the PET studies will be offered participation in the MRI studies. These subjects will undergo a pretreatment MRI and PET scan and a post-treatment MRI and PET scan (i.e., 2 total MRIs, 2 total PET scans, separated by the 8 week clinical trial). Subjects who do not meet imaging selection criteria or who do not wish to undergo scanning will be allowed to participate in the clinical trial portion of the study only. MRI and PET scanning may occur on the same day if this can be scheduled (MRI occurring first, followed by PET scan). However, due to the tightness of scheduling for these scanners, it is more likely that the MRI and PET scans will occur on different days--one day for MRI scan and one day for the PET scan. Typically the MRI scanning day will come before the PET scanning day.

10. MRI of the brain will be acquired using a GE Premier 3.0T System. At the start of the session, a 3-Plane localizer (scout) will be acquired to determine patient position. Subjects will then receive T1-weighted 3D SPGR (Spoiled Gradient Echo), T2 FLAIR, and EPI scans. Acquisition parameters for the EPI scans will be: TE/TR (ms) 20/2000; Flip Angle (deg) 72o; in-plane resolution (voxels) 112x112; slice thickness/gap (mm) 3/0; slices 41.

11. For the MRI procedures, participants are instructed to lie as still as possible within the magnet. The MRI scan is completed in one session, and lasts for a total of 60 minutes. All precautions and protections are given to the participant to ensure that they are as safe and as comfortable as possible. For participants' comfort within the scanner, they lie on a padded table with a pillow to rest their heads on. A blanket is also provided to keep participants warm during the procedure. If the participant appears nervous or anxious, a trained member of the research staff remains with them inside the scanning

suite for the duration of the scan. The participant is given a squeeze ball to terminate the scan at any time. If he/she squeezes the ball, he/she will be removed from the scanner immediately. Participants may decline the MRI scans at any time. If the participant chooses not to be scanned, his/her participation in the study will not be affected. Of course, a structural MRI scan would be required to participate in the PET scans. Any subject who cannot have at least a structural MRI scan would not be able to participate in this protocol. All of the MRI procedures are conducted on the 3-Tesla MRI scanner at the New York State Psychiatric Institute. Conducting these procedures will be an accredited Magnetic Resonance Technologist and one member of the research staff (Bachelor's Level or Higher), or [name] or [name], present.

### PET Scanning

12. The neuroimaging subset of depressed subjects will have 2 [11C]-raclopride PET scans: (1) pre-treatment and (2) post-treatment (at the end of the 8 week duration trial).

13. PET experiments will be conducted with the mCT scanner in the PET Suite on the R1 level of the Public Health Building. Subjects participating in the study will be escorted on PET scan day by a research staff member to the R1 level of the Public Health Building where the PET scanner is located. A research staff person will stay with the subject throughout the procedure. The preparation of the subject will include the placement of a venous catheter.

14. The radiochemistry laboratory and PET suite staff will be in frequent communication regarding the status of preparation of the research subject (such as placement of venous line) and the progress of the radiotracer synthesis. As scan time approaches, the subject will be placed in a supine position on the camera table and will have vital signs (blood pressure and heart rate) obtained. Head will be positioned and a headholder will be used to decrease head movement during the scan.

15. Baseline scan: A low dose CT transmission scan is then obtained prior [11C] raclopride administration. At the end of the transmission scan, a maximum of 14 mCi of [11C] raclopride will be injected intravenously. The dose of [11C] raclopride, diluted in a 10 cc syringe, will be given as a single bolus over a period of 30 seconds. [11C] raclopride will be prepared by the central radio-ligand staff of the PET Center and will be administered by an approved Nuclear Medicine physician (Drs. [name], [name], or [name]). Study physicians will be present for all radiotracer injections. All study physicians have New York State Medical license and have had extensive training and experience with these types of PET studies. [11C] raclopride will be synthesized and tested for purity and sterility according to our standard procedure. The injected dose of [11C]-raclopride for each scan will not exceed 14 mCi, and lower amounts will be permitted. The study physician or Nuclear Medicine physician will evaluate the reconstructed PET image in order to ensure tracer uptake in the brain and will inform the radiochemist if there is a lack of expected uptake in the brain. All subjects will be monitored by the study physician at the time of injection and a study physician or nurse will be present in the PET suite.

16. Post-treatment scan: As close to the end of the 8 week study as possible (based on PET scheduling), subjects will undergo their post treatment scan. We will follow standard procedures for measuring LDOPA-induced changes in synaptic dopamine levels set forth in PET studies of PD patients. Subjects will be given 75mg carbidopa/300mg L-DOPA approximately 1.5 hours before scanning. Subjects in week 8 of the

protocol are taking 450mg LDOPA per day (150mg three times daily), so the 300mg administered prior to the post-treatment PET scan will constitute 300mg of their usual 450mg daily dose on the scan day. A low dose CT transmission scan is obtained prior to intravenous administration of 14mCi [C] raclopride (or less). The start of tracer injection will be timed to coincide with the time of onset of L-DOPA effects (approximately 60-90 minutes following oral dose). Thus, the 60 minute PET scanning session will occur from 90 minutes to 150 minutes following L-DOPA dosing in all subjects. At the completion of the scan the IV catheter will be removed, and the subject will be evaluated (including mental status and vital signs) by a study physician. Vital signs, and physical exam will be performed prior to discharge from the PET suite.

17. Since nausea is a known side effect of L-DOPA, we will be particularly vigilant about monitoring for it. When nausea occurs patients generally feel warm and sick to their stomachs. It will likely occur after PET scanning, but if vomiting were necessary, the MD would remove the subject from the scanner so that vomiting does not occur while supine. Removal from the scanner can occur immediately.

18. PET data will be reconstructed into images using the appropriate reconstruction protocols and filters. PET images will be coregistered to the MRI and regional time activity curves will be measured. Data will be fitted to pharmacokinetic models, and relevant pharmacokinetic parameters, including the percent of receptors engaged by dopamine, will be estimated based on the model fitting procedures.

16. Drs. [name] and [name] continue to be Co-Investigators responsible for neuroimaging as part of a subcontract executed between RFMH and SUNY-Stony Brook. They will lead analyses of neuroimaging data. In terms of on-site execution of PET and MRI scans, these are supervised by the study PI ([name]) and/or [name], who works with the PI as a study clinician and has a research background in PET neuroimaging.

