### Clinical treatment

19. **At each weekly visit, subjects will meet with a psychiatrist of study physician.** At Week 0, subjects will be randomized to L-DOPA vs. placebo according to a blocked randomization schedule developed by the study statisticians and supplied to the NYSPI pharmacy. Raters, clinicians, and participants will be blinded to treatment assignment, though clinicians will be able to break the blind in case of clinical emergency. Treatment allocation will be concealed by over-encapsulation of 25/100 sinemet tablets or placebo tablets, such that all study pills will appear identical. All subjects will take 1 pill three times daily regardless of their treatment assignment. Those assigned to L-DOPA will begin taking 37.5mg carbidopa/150 mg levodopa once daily (with placebo twice daily) for one week, then increase to 75mg carbidopa/300mg levodopa (37.5 mg carbidopa/150mg levodopa twice daily and placebo once daily) for one week, and finally increase to 112.5mg carbidopa/450mg levodopa (37.5 mg carbidopa/150mg levodopa three times daily and no placebo) for the final six weeks. Subjects assigned to placebo will take placebo three times daily throughout the study. The 1.5 25/100 sinemet pills that are needed to make up a dose of 150mg levodopa will be installed a single, overencapsulated pill by the pharmacy.

20. Each subject assigned to the L-DOPA arm will be titrated to 450mg L-DOPA unless they cannot tolerate higher doses, in which case subjects will have their dosage reduced to the maximum tolerable dose. We chose 450mg as the target dose based on its being the dose that met the target progression criteria in the R61

Phase of this project (increased dopamine release in the striatum and increased processing/gait speed) and was highly tolerable to subjects. Both in our Pilot study and the literature overall, L-DOPA is an extremely well tolerated medication at doses < 600mg, which is substantially less than the doses often reached in the treatment of Parkinson's disease (900-1200mg). L-DOPA has been administered to healthy subjects in single dose studies and found to be well-tolerated. In Parkinson's disease, a recent clinical trial published in the New England Journal of Medicine randomized patients to receive 150mg, 300mg, or 600mg L-DOPA for 40 weeks. No dyskinesias or other neuropsychiatric effects were observed that were greater than the placebo group.

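### The pre-scan dosing rule for the post-treatment PET names active L-DOPA for all scanned subjects, which conflicts with placebo allocation and with permitted dose reduction

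*Protocol*

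**What the plan says.** Protocol, PET Scanning, item 16 (post-treatment scan) sets the pre-scan dose: "Subjects will be given 75mg carbidopa/300mg L-DOPA approximately 1.5 hours before scanning". It treats subjects in week 8 as being on 450 mg/day and says that the 300 mg "will constitute 300mg of their usual 450mg daily dose on the scan day". The timing sentence reads: "PET scanning session will occur from 90 minutes to 150 minutes following L-DOPA dosing in all subjects".

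Three other parts of the protocol bear on who is scanned and what they are taking.

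- MRI Scanning, item 9: "The first 30 subjects who are eligible/safe for PET/MRI procedures and are willing to be scanned will be offered participation in these procedures". Arm plays no part in selection. The same item adds: "Subjects who are not willing or able to participate in the PET studies will be offered participation in the MRI studies", so some of the imaging subset may have no PET.
- Clinical treatment, item 19: "Subjects assigned to placebo will take placebo three times daily throughout the study". It also says: "All subjects will take 1 pill three times daily regardless of their treatment assignment". The capsules are over-encapsulated to look identical, and raters, clinicians and participants are blinded.
- Clinical treatment, item 20: if an L-DOPA subject cannot tolerate the higher doses, "subjects will have their dosage reduced to the maximum tolerable dose". The risk-minimisation section (item 2) also allows dose reduction and withdraws a subject only when 37.5/150 mg daily is not tolerated, so 150 mg/day is the lowest dose at which a subject stays in the study.

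The risk-minimisation section (item 3) says that the PET procedures are unchanged for the R33 phase.

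**The concern.** Item 16 describes one kind of subject only: an L-DOPA subject at the full 450 mg/day. The scanned group will also contain placebo subjects and may contain L-DOPA subjects on a reduced dose. The instruction names an active drug and a dose for all of them.

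Three things are at stake if staff follow the text.

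- Placebo subjects would receive active drug against their allocation. It would be a first dose of 300 mg without titration, although the protocol relies on slow titration to limit side effects.
- A dose-reduced subject would receive, in one intake, as much as or more than the daily dose they have been shown to tolerate.
- Hypothesis 2 in Specific Aims relates the post-L-DOPA fall in raclopride binding potential (BP) to symptom improvement. In placebo subjects the BP change would reflect one acute dose, while the HRSD change would reflect eight weeks of placebo. Pooling them with the L-DOPA arm would distort the association.

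**Working it through.** **1. Reproduce the plan's dose statement.** Inputs are from Clinical treatment, item 19, and PET Scanning, item 16. One capsule is 37.5/150 mg.

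- Full daily dose: 3 × 150 = 450 mg.
- Pre-scan dose: 2 × 37.5/150 = 75/300 mg.
- Share of the day: 300/450 = 67%.

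The statement is correct for an L-DOPA subject at full dose.

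**2. Apply the same 300 mg to the other subjects who can be scanned.**

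| Subject at week 8 | Daily L-DOPA | Pre-scan 300 mg relative to the daily dose |
|---|---|---|
| L-DOPA, full dose | 450 mg | 300/450 = 67% |
| L-DOPA, reduced | 300 mg | 300/300 = 100% in one intake |
| L-DOPA, reduced to the floor | 150 mg | 300/150 = 200% in one intake |
| Placebo | 0 mg | 300 mg against 0 mg |

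For a placebo subject, 300 mg is also twice the first-week dose of 150 mg/day with which the L-DOPA arm starts.

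**3. Count the placebo subjects affected.** Inputs are 90 randomised, 45 per arm (SAP, Overview); 30 imaged (MRI Scanning, item 9); 15% drop-out (SAP, Power analysis); and 68 completers of 90 (Description of Subject Population). Assumptions: imaging uptake is unrelated to arm, completion is the same in both arms, and all 30 have PET unless stated.

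The number of placebo subjects among 30 drawn from 90 is hypergeometric.

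- Mean: 30 × 45/90 = 15.
- Variance: 30 × 0.5 × 0.5 × (90 − 30)/(90 − 1) = 5.06, so the SD is 2.25.

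With completion probability p, the mean is 15p and the variance is p² × 5.06 + p(1 − p) × 15.

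| Completion to second scan | Mean | SD | Central 95% range |
|---|---|---|---|
| All (p = 1) | 15 | 2.25 | 11 to 19 |
| p = 0.85 | 12.75 | 2.36 | 8 to 17 |
| p = 68/90 = 0.756 | 11.3 | 2.38 | 7 to 16 |

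If only 20 of the 30 had PET (an assumption, to show the effect of MRI-only participation), the means become 10, 8.5 and 7.6. Blocked randomisation may narrow the ranges. In every case about half of those scanned are placebo subjects.

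**4. Look for reconciling text.** None was found. Item 16 has no arm restriction, placebo equivalent or dose-reduced equivalent. The Clinical treatment section describes one capsule three times daily and no scan-day supply of two at once.

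**5. Check the analysis plan.** SAP Aim 3.2 relates HRSD change to processing and gait speed change only. It contains no BP analysis. The distortion therefore concerns Hypothesis 2 as stated in the protocol, not a specified SAP model.

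**The case against.** The strongest reply is that item 16 is shorthand. The protocol often writes of L-DOPA for everyone when it means study drug: the lay summary and Specific Aims have all 90 receiving L-DOPA, the Assessments section times testing from the morning L-DOPA dose, and the endpoint imaging is called post-L-DOPA. Item 16 itself treats the 300 mg as part of the usual daily dose, which a placebo subject does not have. The only supply described is identical capsules under a blinded schedule, and two of them make 75/300 mg. Giving two study capsules would give placebo subjects placebo.

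This makes blinded capsules the likely intent, and it stands to that extent. It does not cure the text, which names an active drug and dose. Nor does it settle the dose-reduction conflict, which remains even if item 16 covers the L-DOPA arm alone. Blinded staff could not apply an arm-specific rule without pharmacy-prepared packs. A deliberate challenge in everyone is a third possible intent, but it would contradict item 19 and the reference to a usual dose.

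The safety concern is also limited. The protocol's risk section reports that 16 older adults given a single 200 mg dose had no severe side effects and 44% had mild nausea. That dose is lower than 300 mg but relevant, and item 17 provides nausea monitoring. Item 20 calls 450 mg highly tolerable in R61, so dose-reduced subjects are probably few.

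A reader might infer that the literal rule would stop the scans from separating 8-week from acute effects by arm. That does not follow. If both arms had the same acute dose, the placebo arm would show the acute effect, and the difference between arms would show what eight weeks of treatment adds. It is the blinded-capsule rule that combines acute and 8-week exposure in the L-DOPA arm.

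**Conclusion.** The point holds as a conflict in the protocol text that should be fixed. As written, item 16 doses about half of the scanned subjects against allocation: about 15 of 30 if all have PET and complete, and about 11 to 13 with planned attrition. These counts assume uptake unrelated to arm and equal completion, and they fall if some subjects have MRI only. For any dose-reduced subject the single intake is one to two times the tolerated daily dose; the number of such subjects is not given.

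The consequences are off-allocation dosing, dosing above tolerance, and a Hypothesis 2 association in which placebo subjects' BP change reflects an acute dose. The size of that distortion cannot be computed from the documents. The L-DOPA arm's own pre-post displacement would still be measured.

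Two further inferences are not supported. One is that the HRSD primary analysis is compromised, for example because side effects reveal the scan-day dose. The documents do not fix the order of the scan and the Week 8 ratings, so this is not shown. The other is that the sponsor intends to give placebo subjects active drug. The carry-over of wording from R61 is plausible, since the PET procedures are said to be unchanged, but it is also inference.

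**What to change.** Amend PET Scanning, item 16, as follows.

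- Define the pre-scan dose as two of that day's three blinded study capsules, in a pharmacy-labelled scan-day pack made up to the subject's assignment and current tolerated dose: two active (75/300 mg) at 450 mg/day; one active and one placebo (37.5/150 mg) if reduced; two placebo in the placebo arm.
- Reword the timing sentence so that the scan window is counted from study-capsule dosing, not from L-DOPA dosing in everyone.
- Record the dose actually taken before each post-treatment scan.
- State that BP change in the L-DOPA arm reflects acute and 8-week exposure combined.

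If an active challenge in all subjects is really intended, the protocol should say so, reconcile it with the placebo and dose-reduction rules, and label placebo subjects' BP change as an acute-challenge measure.

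The cost is one amended paragraph and scan-day packs for at most 30 subjects, made from capsules the pharmacy already prepares. No scans, visits or patients are added. The downside is that dose-reduced subjects are scanned at 150 mg, so their BP change is not at the same dose as that of full-dose subjects; the recorded dose lets this be taken into account.
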